5.8. Exploratory Endpoints

Exploratory endpoints will be summarized for both the ITT1 and ITT2 analysis sets. Summary statistics by nominal timepoint will be provided for all the exploratory endpoints, including ALS-CBS, EQ5D-5L, and biomarkers (plasma hydroxyeicosatetraenoic acid [HETE], plasma ferritin, 4-hydroxynonenal [4HNE], urine p75 neurotrophin receptor [p75NTR], and cerebrospinal fluid NfL). Values of biomarkers and CSF NfL that are BLQ will be set to half of LLOQ.

ALS-CBS total score will be analyzed using the same methodology described for secondary (continuous) endpoints in Section 5.5.1.1. P-values for the treatment arm comparison at week 24, estimate of LSMEANS for the treatment differences (PTC857 – Placebo), and the two-sided 95% confidence intervals of the LSMEANS difference will be presented.

6. SAFETY ANALYSES

All analyses described in this section will be performed on the Safety Analysis set and will be presented by treatment group (actual treatment received PTC857 vs Placebo). The results will be descriptive in nature. There will be no statistical comparisons between the treatment groups for safety data, unless otherwise specified within the relevant section. All data will be summarized and listed.

Safety assessments will include adverse events, laboratory assessments, vital signs, 12-Lead electrocardiogram, physical examination, and Columbia-Suicide Severity Rating Scale (C-SSRS).

6.1. Extent of Exposure

The extent of exposure to study drug will be summarized descriptively. The summaries will include mean, SD, median, minimum, and maximum values.

The extent of study drug exposure for the double-blind treatment period (Part A) is defined as the difference between the dates of the last dose of study medication and the first dose study drug in the double-blind treatment period plus 1.

6.2. Adverse Events

Adverse events will be collected and recorded from the time subjects sign the informed consent form to the end of the follow-up period. All AEs will be classified by primary system organ class (SOC) and preferred term (PT) according to MedDRA coding dictionary. A treatment-emergent adverse event (TEAE) is an AE that begins after the first administration of study drug or any existing AEs that worsens after the first dose of study drug. All reported AEs will be listed, but only TEAEs will be summarized in tables.

AEs with an onset from day 1 of the double-blind treatment period up to and including 30 days after the last dose of study drug in the double-blind treatment period (or up to and not including the start date of the LTE period whichever comes first) will be considered as occurring during the double-blind treatment period.

An overall summary of TEAEs presenting number and percentage of subjects reporting at least one TEAE for the categories presented below:

- Subjects with at least one TEAE
- Subjects with at least one TEAE related to study drug
- Subjects with at least one serious TEAE
- Subjects with at least one non-serious TEAE
- Subjects with at least one serious TEAE related to study drug
- Subjects with at least one TEAE leading to premature discontinuation of study drug
- Subjects with at least one TEAE leading to death
- TEAEs by highest relationship to study drug
- TEAEs by highest severity

The following summaries will be tabulated:

- TEAEs overall and by SOC and PT
- TEAEs occurring in \geq 5% of subjects within a treatment group, by PT
- TEAEs by PT
- Study drug related TEAEs, overall and by SOC and PT
- TEAEs by maximum severity, overall and by SOC and PT
- Grade 3 or Higher TEAEs by SOC and PT
- Grade 3 or higher related TEAE by SOC and PT
- TEAEs by highest relationship to study drug
- Serious TEAEs, overall and by SOC and PT
- Serious TEAEs, overall and by severity grade, SOC and PT
- Non-serious TEAEs, overall and by severity grade, SOC and PT
- TEAEs leading to discontinuation of study drug, overall and by SOC and PT
- TEAEs leading to death, overall and by SOC and PT

TEAEs with "possibly related", "probably related" or "related" to study drug based on the investigator assessment will be considered as drug related TEAEs. TEAEs with missing causality, if any, will be assumed as 'Related AEs'.

For summaries by SOC and PT, a subject will be counted only once at the SOC level and once at each PT within the SOC level, even if the subject experienced more than one AE within a specific SOC and PT. For summaries by SOC, PT, and maximum severity, a subject will be counted only once at the maximum severity level for which the event occurred at the SOC level and at the maximum severity level for which the event occurred for each unique PT within that SOC level. Therefore, subjects will contribute to only one severity level within a PT or SOC.

Summaries presenting frequency of TEAEs by SOC and PT will be ordered by overall descending frequency of SOC and then, within a SOC, by overall descending frequency of PT. Summaries presenting TEAEs by PT only will be ordered by overall descending frequency of PT.

Subject listings of all adverse events will be provided. Deaths and other serious or clinically significant non-fatal adverse events will be listed separately.

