mucosa of the non-glandular stomach. The no-observed-adverse effect level was determined to be 100 mg/kg/day. There were no dose-limiting toxicities observed in the 1-month monkey toxicology study or in the 3-month rat and monkey toxicology studies.

A 6-month repeat-dose GLP toxicology study was performed in rats with PTC857 at dose levels of 0, 30, 100, and 200 mg/kg/day. Two of the 14 female rats whose mammary glands were examined in the 200 mg/kg/day group at the end-of-dosing necropsy and 1 of the 4 female rats whose mammary glands were examined in the 100 mg/kg/day group at recovery necropsy had mammary gland adenocarcinomas. The no-observed-effect-level (NOEL) for the mammary gland findings was determined to be 30 mg/kg/day in females. AUC exposure multiples at the NOEL dose in females were approximately 2× anticipated clinical exposures. Mammary gland findings in the female rat were observed at ≥9× AUC exposure multiples compared with anticipated clinical exposures. No findings of adenocarcinomas were observed in male rats at any dose level tested. These findings are likely due to a non-genotoxic mechanism of action, since PTC857 was negative in the Ames mutagenicity and in vitro and in vivo micronucleus genotoxicity assays.

A 9-month repeat-dose GLP toxicology study was performed in monkeys with PTC857 at dose levels of 0, 50, 100, and 300 mg/kg/day. There were no PTC857-related microscopic or macroscopic findings at the end of dosing or recovery necropsies, and no PTC857-related mortality occurred. There were no mammary gland findings in this study.

The phototoxic potential of PTC857 was measured by the relative reduction in viability of BALB/c 3T3 mouse fibroblasts exposed to PTC857 with and without ultraviolet radiation. PTC857 demonstrated phototoxic potential in this assay. The phototoxic potential of PTC857 was further evaluated in an in vivo study in Long-Evans rats administered at dose levels of 0, 30, 100, or 300 mg/kg/day for 3 days. Target skin and eye effects were not observed; there was no evidence of phototoxic potential. Hence, measures to protect against sun and ultraviolet light exposure are not necessary with PTC857 treatment.

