^a The Baseline Visit will be defined as Day 1 of the study. Baseline Visit procedures may be performed within the 3 days before the day that study drug is first administered. The day in which the first dose of study drug is administered will be Day 1. For subjects taking part in the PK Sub-Study, the PK laboratory tests must be completed on the same day as the first dose of study drug.

^b Day 169 will be considered the End of Treatment Visit only for those who choose not to enter the LTE Period (Part B).

^c Follow-up Visit on Day 197 only for subjects who choose not to enter the LTE Period (Part B).

^d For subjects who terminate early from the study and consent to continued follow-up, the investigator should attempt to gain vital status on the participant and conduct the ALSFRS-R assessment approximately every 28 days for the remaining duration of the study, in accordance with local requirements/regulations.

- e The Day 29 Visit will be conducted in-person for subjects participating in the PK Sub-Study only.
- f For the telephone call/in-home visits, where applicable, the ALSFRS-R, C-SSRS, adverse events, and prior/concomitant medications assessments will be conducted via a telephone call. Vital signs assessments and samples for clinical laboratory tests will be collected via a home health nurse during applicable inhome visits at the subject's home during these visits. Subjects may go to the site for an in-person visit at the discretion of the PI. Visits indicated as in-person only may be conducted remotely (ie, in-home) following discussion between the site and the medical monitor. In-person visits that are conducted remotely must include the following assessments, at minimum (if such assessments are typically included during the visit): serum/urine pregnancy test (females only), vital signs, clinical laboratory tests, ALSFRS-R, C-SSRS, adverse events, prior/concomitant medications, sparse PK blood sampling, laboratory biomarkers, and ALSAQ-40.
- ⁹ The ICF for Part B should be provided to the subject at the Day 85 visit to allow the subject adequate time to consider transitioning into Part B.
- ^h The ICF for Part B should be signed by the subject at the Day 169 visit if they choose to enroll into Part B.

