- ^u Pulmonary function tests will assess slow vital capacity and Sniff Nasal Inspiratory Pressure. Forced vital capacity, vital capacity, forced expiratory volume, and maximum inspiratory pressure will not be measured. Refer to the laboratory manual for specific requirements at Screening. Oxygen saturation, respiratory rate, and heart rate will be assessed in both upright and supine positions. The Sniff Nasal Inspiratory Pressure test will assess nasal pressure in each unilaterally occluded nostril during a maximal sniff to assess inspiratory muscle strength.

- ^v During the Screening Visit (Day -56), the "baseline" version of the C-SSRS will be administered. At all other visits, the "since last visit" version will be administered.
- w Mammograms to be conducted for female subjects only. A mammogram is not required during the Screening Period if the subject has had a negative breast cancer imaging status (ie, not considered clinically abnormal and/or requiring further evaluation/treatment) within 6 months prior to the Screening Visit. If clinically indicated, an ultrasound or MRI may also be conducted for breast cancer imaging, per the investigator's discretion. If a subject cannot complete the Screening mammogram or any necessary follow-up procedures during the Screening Period, the Screening Period may be extended after discussion and agreement with the medical monitor.
- ^x Women who have been exposed to study drug for at least 3 months and discontinue treatment before reaching the Day 169 Visit will have breast cancer surveillance imaging performed at the Early Termination Visit. Women who have been exposed to study drug for <3 months and discontinue treatment before reaching the Day 169 Visit may have breast cancer surveillance imaging performed at the investigator's discretion.
- ^y The following additional procedures will be conducted only in subjects taking part in the optional PK Sub-Study:
 - Blood samples for riluzole, edaravone, and/or sodium phenylbutyrate/taurursodiol PK will be collected at Day -28 predose (prior to the first dose of riluzole, edaravone, and/or sodium phenylbutyrate/taurursodiol on Day -28) and 1 hour (±15 minutes) post-dose. Subjects should be instructed not to take riluzole, edaravone, and/or sodium phenylbutyrate/taurursodiol on Day -28 prior to the study visit.

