7.3.15. Safety Oversight

An independent DSMB will be utilized during the study. The DSMB will closely monitor potential emerging safety signals in all subjects in the study throughout their study participation, including the planned transition without interruption in treatment from Part A to Part B of the study.

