6.8. Other Safety: Body Weight, BMI, Breast Imaging and Pregnancies

Bodyweight

Bodyweight is assessed at Screening, Day 1, Day 85, and Day 169, as well as the ET visit where applicable. Height is assessed once at the screening visit.

The observed bodyweight and BMI values at each visit, along with the change from baseline to each post-baseline visit will be summarized descriptively as continuous variables by treatment group and overall. The following categorizations will additionally be summarized for body weight at each visit:

Category	Change from Baseline
Category 1	≥ 10% loss
Category 2	≥ 5 - 10% loss
Category 3	-5% < Weight change <+5%
Category 4	≥ 5 - 10% increase
Category 5	≥ 10% increase

Breast Imaging and Pregnancies

Breast imaging for female subjects is conducted at the screening visit and at the day 169 visit. Imaging is not required during the screening period if the subject has had a negative breast cancer imaging status (i.e., not considered clinically abnormal and/or requiring further evaluation/treatment) within 6 months prior to the screening visit. If clinically indicated, an ultrasound or MRI may also be conducted for breast cancer imaging, per the investigator's discretion. Summary statistics will be used to describe the breast imaging results.

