6.3. Adverse Events

6.3.1. Reporting of Adverse Event Data

Adverse events will be collected and recorded from the time subjects sign the informed consent form to the end of the follow-up period. All AEs will be classified by primary system organ class (SOC) and preferred term (PT) according to the MedDRA coding dictionary. A treatment-emergent adverse event (TEAE) is an AE that begins after the first administration of study drug or any existing AEs that worsens after the first dose of study drug. All reported AEs will be listed, but only TEAEs will be summarized in tables.

AEs with an onset from day 1 of the open label long-term extension periods up to and including 30 days after the last dose of study drug in the open label long-term treatment periods (or up to and not including the start date of the Continued LTE period whichever comes first) will be considered as occurring during the LTE treatment period.

An overall summary of TEAEs, including the number and percentage of subjects reporting at least one TEAE for the categories listed below, will be provided.

- Subjects with at least one TEAE
- Subjects with at least one TEAE related to study drug
- Subjects with at least one serious TEAE
- Subjects with at least one non-serious TEAE
- Subjects with at least one serious TEAE related to study drug
- Subjects with at least one TEAE leading to premature discontinuation of study drug
- Subjects with at least one TEAE leading to death
- TEAEs by highest relationship to study drug
- TEAEs by highest severity

The following summaries will be tabulated:

- TEAEs overall and by SOC and PT
- TEAEs occurring in \geq 5% of subjects within a treatment group, by PT
- TEAEs by PT
- Study drug related TEAEs, overall and by SOC and PT
- TEAEs by maximum severity, overall and by SOC and PT
- Grade 3 or Higher TEAEs by SOC and PT
- Grade 3 or higher related TEAE by SOC and PT
- TEAEs by highest relationship to study drug
- Serious TEAEs, overall and by SOC and PT
- Serious TEAEs, overall and by severity grade, SOC and PT
- Non-serious TEAEs, overall and by severity grade, SOC and PT
- TEAEs leading to discontinuation of study drug, overall and by SOC and PT
- TEAEs leading to death, overall and by SOC and PT

TEAEs with "possibly related", "probably related" or "related" to study drug based on the investigator assessment will be considered as drug related TEAEs. TEAEs with missing causality, if any, will be assumed as 'Related AEs'.

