6.9. Body Weight, BMI, Breast Imaging and Pregnancies

Bodyweight and BMI

Bodyweight is assessed at Screening, Day 1, Day 85, Day 169, Day 253, Day 365, Day 533, Day 701, Day 869 and Day 1037 as well as the ET visit where applicable. Height is assessed once at the screening visit.

The observed bodyweight and BMI values at each visit, along with the change from baseline to each post-baseline visit will be summarized descriptively as continuous variables by treatment group and overall. The following abnormality categorizations will additionally be summarized for body weight at each visit:

Category	Change from Baseline
Category 1	≥ 10% loss
Category 2	≥ 5 - 10% loss
Category 3	-5% < Weight change <+5%
Category 4	>5 - 10% increase
Category 5	≥ 10% increase

Breast Imaging and Pregnancies

At the investigator's discretion, an ultrasound or MRI may be performed for breast imaging in female subjects if clinically indicated. These examinations will take place on study days 169, 365, 701, and 1121.

Summary statistics will be used to describe the breast imaging results.

Pregnancy test results will be listed.

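### For women who enter the extension, a breast AE found at the Day 169 mammogram and dated on or after the first open-label dose leaves the Part A AE tables and counts in the PTC857 period

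*SAP*

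**What the plan says.** **Why breast imaging is there.** Protocol 1.4.1 reports that some female rats at 100 and 200 mg/kg/day "had mammary gland adenocarcinomas". Version 3.0 of the protocol then added breast imaging and breast-cancer exclusions (Protocol 14.4).

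**When it is done.** SAP (Part A) 6.8: "Breast imaging for female subjects is conducted at the screening visit and at the day 169 visit". Women with at least 3 months of exposure who "discontinue treatment before reaching the Day 169 Visit will have breast cancer surveillance imaging performed at the Early Termination Visit" (Protocol 3.2, Table 1 footnotes).

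**What else happens on Day 169.** "The ICF for Part B should be signed by the subject at the Day 169 visit if they choose to enroll into Part B" (same footnotes). Protocol Table 2 dispenses Part B drug at this visit and lists the Day 169 mammogram again. Protocol 7.3.15 has the DSMB monitor throughout participation, "including the planned transition without interruption in treatment from Part A to Part B of the study". Extension SAP 3.2.2 sets Day 169 as week 0 of PTC857 exposure for former placebo subjects.

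**How AEs are assigned.** SAP (Part A) 6.2 closes the Part A window 30 days after the last double-blind dose, "or up to and not including the start date of the LTE period whichever comes first". Extension SAP 6.3.1 starts its window with "AEs with an onset from day 1 of the open label long-term extension periods up to and including 30 days after the last dose".

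**Who reports the Day 169 image.** SAP (Part A) 6.8 promises summary statistics of breast-imaging results, and section 6 presents its analyses by PTC857 versus placebo. Extension SAP 6.9 also lists the day: "These examinations will take place on study days 169, 365, 701, and 1121".

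**The concern.** The Day 169 image looks back over 24 weeks of randomised treatment, but any AE arising from it is allocated by onset date. For a woman who continues, that date can easily be the first day of open-label drug or later. The event then belongs to the extension, although the lesion was present before, or at most on, the first open-label day.

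Two things are at stake. Diagnosis, seriousness, severity and relatedness are tabulated through the AE tables, so the randomised comparison of those attributes loses the event. In a former placebo woman, a lesion that arose on placebo is then counted among PTC857-exposed subjects wherever the extension SAP pools without arm labels. No other rule corrects this. Protocol 7.3.3 asks for an onset date without saying how to date an imaging finding, and Protocol 7.3.13 names no AE of special interest.

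**Working it through.** **1. The plan's own dates.** Part A ends on Day 24 × 7 + 1 = 169. Weeks since first PTC857 for former placebo subjects at that visit: (169 − 169)/7 = 0, as in extension SAP 3.2.2. Part B ends on Day 169 + 28 × 7 = 365 and Part C on Day 365 + 108 × 7 = 1121, matching the protocol visit days.

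**2. The window rule.** Let *L* be the last double-blind dose day and *E* the extension start. I read *E* as the first open-label dose, because SAP (Part A) 3.2.5 ends the double-blind period the day before it. An AE is in Part A if 1 ≤ onset ≤ *L* + 30 and, for an entrant, onset < *E*.

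| Woman | Onset | L | E | Part A? |
|---|---|---|---|---|
| Entrant, dated to Day 169 image, drug same day | 169 | 168 | 169 | No |
| Entrant, dated to later work-up | 190 | 168 | 169 | No |
| Entrant, imaged early in the ±3-day window | 166 | 168 | 169 | Yes |
| Entrant, imaged Day 169, first open-label dose next day | 169 | 169 | 170 | Yes |
| Non-entrant, dated to image | 169 | 168 | none | Yes |
| Non-entrant, dated to work-up | 190 | 168 | none | Yes |
| Early termination image | 120 | 118 | none | Yes |

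Non-entrants keep the ordinary 30-day limit, here Day 168 + 30 = 198. Days 166, 190 and 120 and the dose days are illustrations.

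**3. Where the event goes in a former placebo woman.**

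| Display | Treatment of the event |
|---|---|
| Part A TEAE and EAIR tables (6.2, 6.2.1) | Absent |
| Part A imaging summary (6.8) | Kept, under placebo |
| Extension-only tables (6.1.1, 6.3.1) | Shown under Placebo/Utreloxastat |
| Pooled A+B+C tables (6.1.1) | In the single PTC857-exposed column |
| PTC857-exposed EAIR (6.3.2) | Counted, with time starting at first PTC857 |

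In that EAIR, a Day 190 onset contributes 190 − 169 = 21 days from first exposure, and a Day 169 onset essentially none.

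**4. Size.** The documents give neither the share of women nor extension uptake. Assume 340 randomised 2:1, women *f* = 0.30–0.50, entry *e* = 0.70–0.95 and equal across arms.

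- Placebo women: 340/3 × *f* = 34 to 57. PTC857 women: 2 × 340/3 × *f* = 68 to 113.
- Events moved per 1% detection rate = women × *e* × 0.01, if every onset is dated on or after the first open-label dose.

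| f | e | Placebo | PTC857 |
|---|---|---|---|
| 0.30 | 0.70 | 0.24 | 0.48 |
| 0.30 | 0.95 | 0.32 | 0.65 |
| 0.50 | 0.70 | 0.40 | 0.79 |
| 0.50 | 0.95 | 0.54 | 1.08 |

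On that dating and with the same detection rate in entrants and non-entrants, 70–95% of Day-169-detected breast AEs leave the Part A AE tables. With no drug effect, one third of those moved are in former placebo women.

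**The case against.** A reader might infer that these lesions vanish from the PTC857–placebo comparison altogether, or that the extension tables credit placebo-period lesions to PTC857 throughout. The documents support neither. SAP (Part A) 6.8, read with the opening of section 6, still summarises the Day 169 images by arm whatever the AE date. All AEs are listed, with deaths and serious or clinically significant events listed separately. The extension-only tables give former placebo subjects their own column. Arms merge only in the pooled A+B+C column and the PTC857-exposed EAIR.

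The effect also depends on how onset is dated, which the documents leave open; dating to a biopsy weeks later is a scenario. Safety analyses are descriptive, the DSMB watches the transition, and counts this small can be read case by case. Finally, the Day 169 entry in extension SAP 6.9 follows a sentence on discretionary ultrasound or MRI, so it is not a clear claim to the mammogram as an extension outcome.

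All of this stands, and it limits the point. It does not remove it. The imaging summary is a single sentence, with no result categories and no link to histology, so it cannot replace the AE tables for diagnosis, seriousness or relatedness. The ambiguity over who owns the Day 169 image is itself a reason to reconcile the two SAPs. With expected counts near or below one, a single misassigned cancer would change how the pooled PTC857 total reads.

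**Conclusion.** The concern holds in a limited form. It affects women who enter the extension and whose breast AE, found at Day 169, is dated on or after the first open-label dose. Those events leave the Part A TEAE and EAIR tables by a stated rule and fall into the extension period. In former placebo women they also enter two PTC857-exposed displays without an arm label, although they arose before any meaningful PTC857 exposure. The imaging summary and the extension-only tables still allow the original arm to be recovered.

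The expected size is about 0.2–0.5 placebo and 0.5–1.1 PTC857 events per 1% detection rate. This rests on assumed shares of women and extension entry, equal entry by arm, and every onset dated on or after the first open-label dose. Images or onsets dated earlier reduce it. It is worth correcting because breast imaging was added for this specific signal and the correction is cheap, not because many events are at risk.

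**What to change.** Analysis text only; no visit, dose or clinical rule changes.

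1. In SAP (Part A) 6.2 and 6.2.1 and extension SAP 6.3.1 and 6.3.2, assign breast neoplasm and abnormal breast-imaging AEs first shown on the end-of-Part-A (Day 169) image, including diagnoses from its work-up, to the Part A treatment, whatever onset date is recorded.
2. In former placebo women, exclude these events from the pooled PTC857-exposed tables and the PTC857-exposed EAIR.
3. Flag any Day 169 image taken after the first open-label dose and list the interval between them, so that prior open-label exposure is visible.
4. Reconcile SAP (Part A) 6.8 with extension SAP 6.9: the Day 169 image is a Part A outcome and serves in the extension only as the pre-PTC857 baseline for former placebo women. This agrees with week 0 in extension SAP 3.2.2.

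Cost: a few sentences in each SAP. The rule needs only image dates and results, dosing dates and AE records, all within data the study already collects.
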